2. LIST OF ABBREVIATIONS

Abbreviation	Definition
AE	adverse event
ALK	anaplastic lymphoma kinase
BSA	body surface area
DCT	data collection tool
DSU	drug safety unit
EDC	electronic data capture
HCP	healthcare professional
IEC	independent ethics committee
IRB	institutional review board
MedDRA	Medical Dictionary for Regulatory Activities
NANT	New Agents in Neuroblastoma Therapy consortium
NB	neuroblastoma
OS	overall survival
RWD	real world data
SAE	serious adverse event
SD	standard deviation
SIOPEN	European SIOP Neuroblastoma Group
SQN	Syne Qua Non Limited
TKI	tyrosine kinase inhibitor
US	United States

PFIZER CONFIDENTIAL

[figure not shown]

4. AMENDMENTS AND UPDATES

None

PFIZER CONFIDENTIAL

5. MILESTONES

Milestone	Planned date
Start of data collection	25 February 2021
Treatment completed population – data collection completion date	25 March 2021
Progress report – Treatment completed population	28 April 2021
Interim report 1 – Year 1	31 December 2021
Interim report 2 – Year 2	31 December 2022
End of data collection (Last patient added to real world data collection)	31 December 2023
Database lock	15 February 2024
Final study report	31 March 2024

[figure not shown]

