8.2. Setting

Clinical practice and treatment of each patient will follow as determined by each treating HCP individually. There will be no interference from Pfizer with the HCP's diagnostic and treatment decisions. The decision to treat a patient with lorlatinib will be prior to and independent of participation in the real world data collection and according to the clinical judgement of their HCP. Therefore, the data collection will in no way influence prescribing patterns or treatment decisions. If eligible, the patient will receive treatment through Pfizer's expanded access program independent of involvement in the collection of real world data.

HCPs treating a patient approved to receive lorlatinib via Pfizer's expanded access program will be invited to take part in the real world data collection. Upon HCP agreement, they will receive access to the EDC, where they can enter data into the DCT.

The first pediatric neuroblastoma patient received lorlatinib in March 2017 as part of expanded access programs and the program is ongoing. Data collection is anticipated to initiate in January 2021 and is estimated to have last patient entered into real world dataset at

PFIZER CONFIDENTIAL

the end in December 2023. Database lock would occur in February 2024, as outlined in [Section 5](#).

Data will be collected via DCT at multiple time points for patients who are receiving ongoing treatment. These timepoints will be determined by HCP standard practice for treatment and follow-up of their patients. Visits are anticipated to occur every 3-4 months, corresponding with re-supply of lorlatinib. Data will be collected on a continual basis until discontinuation of treatment with lorlatinib, death, loss to follow-up or end of study, whichever comes first.

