8.2.1. Inclusion criteria

Patients must meet all the following inclusion criteria to be eligible for inclusion in the study:

1. Patient treatment with lorlatinib is initiated through Pfizer's expanded access program for treatment of ALK+ neuroblastoma.
2. HCP documentation of at least one tumor assessment of response after patient has had at least one dose of lorlatinib
3. Evidence of a personally signed and dated informed consent document indicating that the patient (or a legally acceptable representative, or a waiver of informed consent has been granted by the IRB/IEC) has been informed of all pertinent aspects of the study.

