Partial Response (PR)	PR in at least one component and all other components are either CR, MD (Bone marrow), PR (Soft tissue or Bone) or Not involved (NI); no component with PD.													
Minor Response (MR)	PR or CR in at least one component but at least one other component with SD; no component with PD.													
Stable Disease (SD)	SD in one component with no better than SD or NI in any other component; no component with PD.													
Progressive Disease (PD)	Any component with PD													
Best Overall response	HCP Reported Response	Derived as the best overall response taking the HCP Reported Response observed up to the data cut-off date for a specific milestone. (The												

PFIZER CONFIDENTIAL

	Repeated using Derived Objective Response	sequence order from best to worst is CR, PR, MR, SD, PD.)
Overall Response Rate (ORR)	Best Overall Response	Derived as Best overall response of CR+PR of the total population observed up to the data cut-off date for a specific milestone.
Duration of response	Treatment Start and HCP Reported Response Date	Derived as (Date of PD or death, whichever occurs first) – (Date of PR or CR, whichever occurs first) + 1
Progression free survival (PFS)	Treatment Start and HCP Reported PD/Death Date	Derived as (Date of PD or death (by any cause in the absence of PD)) – (Treatment start date) + 1
Duration of treatment	Treatment Start and Stop Dates	Derived as (Treatment stop date) – (Treatment start date) + 1
Overall survival (OS)	Treatment Start and Death Dates	Derived as (Date of death) – (Treatment start date) + 1

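### ORR is taken over the total population at each cut-off with no minimum follow-up, so patients who started lorlatinib shortly before a cut-off modestly lower it

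*Combined protocol and SAP*

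**What the plan says.** **Timing.** Section 5 (Milestones) dates one row, "End of data collection (Last patient added to real world data collection", at 31 December 2023, with database lock on "15 February 2024". Section 8.2 also places the last entry in December 2023. On visits, Section 8.2 states: "Visits are anticipated to occur every 3-4 months, corresponding with re-supply of lorlatinib". It sets only an upper limit to follow-up: "Data will be collected on a continual basis until discontinuation of treatment with lorlatinib, death, loss to follow-up or end of study, whichever comes first". No minimum time from first dose to cut-off appears for the interim or final reports.

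**Who can be added.** Section 8.1 admits patients who have completed treatment, patients still on treatment and new patients. Inclusion criterion 2 (Section 8.2.1) requires "HCP documentation of at least one tumor assessment of response after patient has had at least one dose of lorlatinib", with no minimum time on treatment. Section 8.7.2 then bases the summaries on all collected data, whether or not the criteria are met.

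**Endpoint.** ORR in Section 8.7.5 is "Derived as Best overall response of CR+PR of the total population observed up to the data cut-off date for a specific milestone". Section 8.7.6 adds a Clopper-Pearson 95% interval. It gives censoring rules for duration of response, duration of treatment, PFS and OS, and no corresponding rule for BOR or ORR. Section 8.7.8 imputes partial dates only and does not say how a patient without a response assessment counts in ORR.

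**The concern.** The Kaplan-Meier endpoints deal with short follow-up by censoring. A proportion with a fixed denominator has no such mechanism. A patient who began lorlatinib a few weeks before a cut-off is in the ORR denominator at once, but can reach the numerator only after an assessment late enough to show a response. Until then the patient counts as a non-responder, or is classified by one early reading, because of when treatment began.

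HCP-reported response is one of the effectiveness measures in Objective 2, and Section 11 intends the results for regulatory authorities as needed and for publication. The effect on ORR is directional, is not reflected in the Clopper-Pearson interval, and depends on recent accrual. ORR could therefore move between the cumulative annual reports with no change in drug effect. BOR is also split by baseline disease status, and in those smaller groups one or two patients matter more.

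**Working it through.** The plan states no ORR assumption or sample-size figure to reproduce (Section 8.5 says no power calculation was done). The check is date arithmetic followed by a dilution calculation.

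**Inputs from the documents**
- Last patient added and end of data collection: 31 December 2023; lock: 15 February 2024 (Section 5).
- Visit interval: 3-4 months (Section 8.2).
- Maximum N: 50 (Section 8.1).
- First patient treated: March 2017 (Section 8.2); data collection opens 25 February 2021 (Section 5).
- Response rates of 20-64% in earlier relapsed/refractory trials (Section 6), used for illustration only.

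**Assumptions, not in the documents**
- N reaches 50 and treatment starts are evenly spread.
- Patients who started within the last visit interval have no response recorded yet.
- True ORR is 20%, 40% or 64%.

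**Step 1: the gap.** From 31 December 2023 to 15 February 2024 is 46 days, about 1.5 months. One visit interval is 3 × 30.44 = 91 days to 4 × 30.44 = 122 days. The time to lock does not cover one interval.

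**Step 2: expected recent starters at the final cut-off.** k = N × m / T, where m is the visit interval and T the months over which starts are spread.

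| T (months) | m = 3 | m = 4 |
|---|---|---|
| 82.0 (March 2017 to December 2023) | 50 × 3/82.0 = 1.8 | 50 × 4/82.0 = 2.4 |
| 34.1 (25 February 2021 to 31 December 2023) | 50 × 3/34.1 = 4.4 | 50 × 4/34.1 = 5.9 |

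So k is about 2 to 6. The 34-month row is an upper-end case: it puts every start after data collection opened, whereas the plan also expects patients treated before then.

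**Step 3: dilution.** Reported ORR = p × (50 − k)/50.

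| Assumed true ORR | k = 2 | k = 6 |
|---|---|---|
| 20% | 19.2% | 17.6% |
| 40% | 38.4% | 35.2% |
| 64% | 61.4% | 56.3% |

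The relative loss is k/50, or 4% to 12%. In absolute terms it runs from 0.8 points (20%, k = 2) to 7.7 points (64%, k = 6).

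**Step 4: change between reports.** Section 5 gives interim report dates but no interim cut-off dates. Suppose the first interim cut-off were 31 December 2021, 58 months after March 2017, with all treated patients already entered. With 82-month even starts and m = 4, the recent share is 4/58 = 6.9% at that interim against 4/82 = 4.9% at the end. A true 40% would read 0.40 × (1 − 4/58) = 37.2% and then 0.40 × (1 − 4/82) = 38.0%. Uneven accrual could make the difference larger or smaller.

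**Step 5: what a restricted ORR costs in precision.** Take 5 recent starters without a response and 18 responders among the other 45. The all-patient ORR is 18/50 = 36.0% (Clopper-Pearson 95% CI 22.9 to 50.8, width 27.9 points). The restricted ORR is 18/45 = 40.0% (25.7 to 55.7, width 30.0 points).

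**The case against.** **An eligible patient must already have an assessment.** Criterion 2 would keep a never-assessed patient out. This stands in part. A reader might infer that late starters always sit in the denominator with no reading at all, and the eligibility rule does not support that. It does not remove the problem, because one assessment at any time after one dose satisfies it, and Section 8.7.2 summarises patients who fail it as well.

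**Added is not started.** This stands. A reader might take the shared milestone date to mean that the last patients have no follow-up. A patient added on 31 December 2023 may have started long before and arrive with a full chart history. Only recent treatment starts matter, and the documents do not say how many there will be.

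**The size could be overstated.** A reader might assume that nobody within 6 months of a cut-off can have responded. The plan's own visit interval does not support this, since patients 4 to 6 months into treatment should have had a visit. The estimate is therefore limited to the last 3-4 months. Even there, an unscheduled early assessment could show a response, so the figures are upper values for a given k.

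**The net direction is not certain.** Enforcing criterion 2 would drop patients who die or stop before any assessment, which pushes ORR up. That is a separate effect. The claim here concerns only the short-follow-up component, which is downward.

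**The study is descriptive.** There is no hypothesis test or decision threshold, the plan does not rank ORR as its main result, and later cumulative reports update the best response of patients who were recent at an interim. An all-patient ORR is a defensible conservative summary. All of this limits the importance of the point, but an estimate can be biased without being tested.

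**Conclusion.** The point holds as a modest one. ORR and BOR have no minimum-follow-up rule, entry of new patients runs to the end of data collection, and neither criterion 2 nor the analysis set prevents recent starters from being counted as non-responders or by a single early reading.

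With 50 patients, even starts and no response yet among those in their first 3-4 months, an assumed true 40% would read about 38% (starts over 82 months) to 35% (over 34 months). That is small beside the sampling uncertainty: 20/50 has a 95% interval of 26.4% to 54.8%. It is nevertheless directional and can vary with recent accrual. The true size depends on the unknown number of recent starters and on how early they are assessed.

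The documents do not support the stronger readings that every patient added late lacks follow-up, that the final ORR is biased downward overall, or that the study's principal result is compromised.

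**What to change.** In Sections 8.7.5 and 8.7.6, add that at each milestone BOR and ORR, with the Clopper-Pearson interval, will also be reported for patients whose first lorlatinib dose was at least a pre-stated time before the cut-off. Six months is one example, being more than one visit interval. It is not a value from the documents, and the sponsor may justify another. Show this beside the all-patient ORR, and state the cut-off date for each milestone.

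Select by start date only, never by whether an assessment took place. Selecting on assessment would drop patients who die or stop early and would bias ORR upward. Keep all patients in the Kaplan-Meier and safety summaries.

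Closing entry early, for example to patients starting after 30 June 2023, might look equivalent but is not. It would help only the final report, would remove patients from the Kaplan-Meier and safety summaries, and would run against the Section 8.5 aim of including every eligible patient.

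The cost is a sentence or two in the plan, one extra analysis from data already collected, and a slightly wider interval for the restricted ORR. With a 6-month rule and even starts, about 50 × 6/82.0 = 3.7 patients would fall outside the restricted set at the final cut-off, or 50 × 6/34.1 = 8.8 in the upper-end case.

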6. RATIONALE AND BACKGROUND

Neuroblastoma (NB) is an aggressive solid tumor of childhood. Neuroblastoma is the third most common childhood cancer in the United States and accounts for 7-10% of pediatric cancers.¹ Estimated incidence of neuroblastoma is approximately 10-11 cases per million children under 15 years of age United States (US) and Europe.^{2,3} Incidence in children <1 year is as high as 44.7 per million in Europe and 53 per million in US.² Neuroblastoma is most commonly diagnosed during the first year of life.^{1,2} While 90% of cases are diagnosed before the age of 5, 30% of those are within the first year. The median age of diagnosis is 22 months. Rarely does it present in adolescence and adulthood, but outcomes are much poorer in this age group.⁴ In addition, neuroblastoma accounts for approximately 12% of all cancer-related deaths in pediatric population.^{5,6}

Five-year survival rates for infants with neuroblastoma range from 65% to 88% and overall survival has improved over time, likely due to therapeutic improvements.^{1,3,5,7} However, improvements are attributable to improvement in patients with more low or intermediate-risk disease, mortality rates among children with high-risk neuroblastoma have shown modest improvement.⁸

Neuroblastoma is a complex disease but often results in treatment-resistant progression, metastasis and death.⁸ Long-term survival rates for children with high-risk neuroblastoma are currently 40-50%.⁸ Many patients (50-60%) with high-risk neuroblastoma will have either

PFIZER CONFIDENTIAL

refractory disease (responding poorly to therapy) or will relapse (experience disease recurrence). To date there are no well-established curative treatment regimens for these patients.^{8,9} Median time to relapse is estimated to be approximately 13 months, and patients who relapsed between 6 and 18 months after diagnosis have the highest risk of death.¹⁰

Current treatment approach for high-risk patients include induction chemotherapy (reduce tumor burden by shrinking tumor), local control (delayed surgery to remove tumor), consolidation (myeloablative therapy with stem cell rescue performed in tandem) and maintenance therapy (GD2-directed therapy, which is painful and toxic).¹¹ A published meta-analysis of three European SIOP Neuroblastoma Group (SIOPEN) trials on standard backbone chemotherapy regimens showed poor outcomes in both relapsed and refractory neuroblastoma patients.¹² It is important to note that, unlike childhood leukemias, there is no standard approach for high-risk neuroblastoma patients who suffer a relapse and there is no known curative therapy. Response rates in clinical trials of relapsed/refractory neuroblastoma ranged from 20-64%.¹² After treatment, progression occurred in 54% of patients with refractory disease versus 87% of patients with relapsed disease.¹² Overall median OS was 16.1 months, with longer median OS for patients with refractory disease compared to relapsed disease.¹² Neuroblastoma has significant heterogeneity, therefore risk stratification has become an important factor in identifying novel biomarkers to inform treatment decisions.⁹

Initial reports of anaplastic lymphoma kinase (ALK) gene amplification and overexpression suggested a role of ALK in neuroblastoma.^{13,14} Notably, ALK activating mutations were first discovered in the germline of families where the disease is inherited, and subsequently found to be present in somatic tissue in ~10% of patients at diagnosis.¹⁵⁻¹⁸ The majority of patients with familial neuroblastoma have germline mutations in ALK.¹⁸ Sporadic neuroblastoma tumors also occasionally harbor ALK abnormalities, including 4% of tumors with genomic amplification and approximately 10% with missense mutations.^{14,17-19} Furthermore, the presence of ALK mutation correlates with worse prognosis in high and intermediate risk patients.²⁰ The detection of ALK mutations and/or amplifications in primary neuroblastomas, provides a molecular rational for targeted therapy of neuroblastoma.¹⁶ It has been demonstrated that downregulation of ALK suppressed proliferation of neuroblastoma cells harboring mutated ALK.¹⁵

The identification of ALK as a critical factor in the development of neuroblastoma make it an attractive therapeutic target. Lorlatinib is a potent, brain-penetrant, third generation inhibitor of ALK.²¹ Lorlatinib overcomes almost all known ALK resistance mutations observed with other ALK TKIs.²² In preclinical models lorlatinib has exhibited superior potency towards ALK neuroblastoma tumor models.^{23,24} In addition, lorlatinib shows strong activity toward all tested ALK neuroblastoma mutations.^{23,24}

New Agents in Neuroblastoma Therapy (NANT) consortium has several ongoing clinical trials to identify best therapies and combination of therapies for treatment of pediatric patients with neuroblastoma. An on-going Phase 1 dose escalation clinical trial is assessing

PFIZER CONFIDENTIAL

the use of lorlatinib as a single agent in combination with chemotherapy in patients aged 1 to 90 years with relapsed/refractory neuroblastoma.²⁵ Recently presented results of this Phase 1 study showed inhibition of ALK driven neuroblastoma with lorlatinib occurred with manageable toxicity and objective anti-tumor activity was observed.²⁶

Pediatric high-risk neuroblastoma remains an area of high unmet need and poor outcomes in young children. Along with the promising early clinical data from the NANT study, we have noted several pediatric neuroblastoma patients being treated through Pfizer's expanded access program. This protocol details the real world data collection of data to evaluate the real world effectiveness of lorlatinib in pediatric neuroblastoma patients. Generating real world evidence from expanded access programs is becoming increasingly valuable, as this data has the potential to supplement regulatory submissions.²⁷

7. RESEARCH QUESTIONS AND OBJECTIVES

The primary goal of the Pfizer expanded access program is to provide access to lorlatinib to patients with a serious or immediately life-threatening disease/condition who have exhausted all other standards of care and are not eligible for a clinical trial. Treatment is delivered by the healthcare professional (HCP) as sponsor of the expanded access request and according to a treatment plan approved institutional review board/independent ethics committee as required by local laws and regulations or institutional requirements.

The overall goal of this real-world data collection is to assess demographic, clinical characteristics and real-world effectiveness of pediatric neuroblastoma patients who initiated treatment with lorlatinib through an expanded access program. Data will be collected to address the following specific objectives:

1. Describe the demographic and clinical characteristics of pediatric neuroblastoma patients who initiated treatment with lorlatinib through an expanded access program
2. Evaluate the effectiveness of treatment with lorlatinib in pediatric neuroblastoma patients in terms of duration of treatment, HCP reported response, and duration of response
3. Estimate progression free survival and overall survival
4. Collection of safety data

8. METHODOLOGY FOR REAL WORLD DATA COLLECTION

The real world data (RWD) evaluation will involve supplemental collection of de-identified data collected on patients treated with lorlatinib for pediatric neuroblastoma who initiated treatment through Pfizer's expanded access program. Pediatric patients with ALK-aberrant neuroblastoma who are prescribed lorlatinib by their healthcare professionals (HCPs) and have met Pfizer expanded access program criteria will be eligible for inclusion in data collection. Supplementary data will be collected in partnership with Bionical Emas.

PFIZER CONFIDENTIAL

Prior to initiation of data collection activities, Bonical Emas, in collaboration with Pfizer, will develop a customized data collection tool (DCT) to capture data on demographics, clinical characteristics and outcomes. The length of the DCT will be kept to a minimum to avoid burden on participating institutions. The DCT will be made available to participating institutions through a web-based, electronic data capture (EDC) system.

During data collection, Bonical Emas will review the data on an ongoing basis, with HCPs contacted for clarification as required. Bonical Emas in conjunction with their statistical partner Syne Qua Non Limited (SQN) will summarize and report the data at timepoints detailed in [Section 5](#). Finally, a data collection report will be developed.

8.1. Design of data collection

Up to 50 pediatric patients with ALK-aberrant neuroblastoma who initiated treatment with lorlatinib as part of expanded access program will be included.

The real world data collection will be initiated after the patient has been approved for expanded access to lorlatinib per Pfizer's expanded access program and the treating HCP has agreed to participate in data collection. All assessments described in this protocol are performed as part of normal clinical practice or standard practice guidelines for the patient population and healthcare provider specialty in the countries where this data collection is being conducted. Data from patients who have completed treatment, patients receiving ongoing treatment and new patients will be captured. A progress report will be developed for the patients who have completed treatment, with a more comprehensive final report descriptive in nature produced for the total population.

[figure not shown]
